5 TREATMENT PLAN

Treatment will be administered on an outpatient basis. Expected toxicities and potential risks as well as dose modifications for NeoVax are described in Section 6 (Expected Toxicities and Dosing Delays/Dose Modification). No investigational or commercial agents or therapies other than those described below may be administered with the intent to treat the patient's malignancy.

Patients with clinically evident locoregional metastatic disease or fully resectable distant metastatic disease as defined in 3.1.3 will be identified and enrolled on the study. After signing consent, the patients will undergo surgery with the intention to remove all melanoma (curative intent). Tissue procurement will be performed as described in 5.1. After confirmation of complete tumor resection by pathologic review and determination of adequacy of DNA and RNA yield from tumor tissue for sequencing, the generation of the vaccine as described in 5.2.1 will be initiated. Patients with tumors that are not completely resected and/or that provide inadequate DNA and/or RNA for sequencing will be removed from the trial and replaced.

CONFIDENTIAL

This document is confidential. Do not disclose or use except as authorized.

5.1 Tissue procurement and sequencing

5.1.1 Tumor and normal tissue harvest

Patients will undergo complete resection of their primary melanoma (if not already removed) and all regional metastatic disease with the intent of rendering them free of melanoma. [name], the principal investigator [REDACTED]

[REDACTED] should be contacted at the time of the initial consent to ensure that ancillary studies are coordinated. The study investigators and members of the study team will coordinate tissue acquisition with the surgical staff of the participating institution and the staff of the DFCI/Cell Manipulation Core Facility.

After adequate tumor for pathological assessment has been harvested as deemed by the surgeon, remaining tumor tissue will be placed in sterile media in a sterile container and transferred to the DFCI/Cell Manipulation Core Facility for disaggregation. Portions of the tumor tissue will be used for whole-exome and transcriptome sequencing and cell line and tumor infiltrating lymphocyte generation and any remaining tumor will be cryopreserved or given to the sponsor for protocol-related studies. In the event that sequence analysis yields no results or sub-optimal results, tumor cell line cells or paraffin embedded samples retained by the participating institutions pathology department may be used to prepare additional nucleic acid for sequencing. No saved samples will be used to prepare cellular products for future clinical use. Peripheral blood mononuclear cells from a blood draw will be utilized for a normal tissue sample.

5.1.2 Nucleic acid will be extracted from the tissue samples and sequencing will be conducted at the CLIA-certified laboratory at Broad Institute. For tumor and normal DNA samples, whole exome capture will be conducted prior to sequencing on Illumina HiSeq. For tumor RNA, a cDNA library will be prepared on poly-A selected RNA prior to sequencing on Illumina HiSeq. If the quantity or quality of DNA or RNA isolated from the tissue sample is inadequate for exome or cDNA library preparation and sequencing, then DNA or RNA may be extracted from the patient-specific tumor cell line (if generated) or paraffin embedded samples.

5.2 Preparation of NeoVax

[figure not shown]
5.2.1 Preparation of personalized neoantigen peptides

5.2.1.1 Identification of target epitopes for peptide design

[figure not shown]
[REDACTED]
[REDACTED]
[REDACTED]
[REDACTED]
[REDACTED]
[REDACTED]
[REDACTED]

CONFIDENTIAL

This document is confidential. Do not disclose or use except as authorized.

5.2.1.2 Peptide synthesis

CONFIDENTIAL

This document is confidential. Do not disclose or use except as authorized.

5.2.2 Preparation of NeoVax peptide pools

A decorative horizontal bar at the bottom of the page, consisting of four thick, dark horizontal lines.

5.2.3 Pretreatment criteria

Preparation of the final NeoVax product will begin upon confirmation that the patient is medically cleared to undergo vaccine administration (confirmed arrival in the clinic,

CONFIDENTIAL

CONFIDENTIAL
This document is confidential. Do not disclose or use except as authorized.

stable vital signs, no new acute medical issues or laboratory abnormalities potentially interfering with vaccine administration).

5.2.3.1 Day 1

Laboratory parameters must be reviewed and must be within the ranges as listed in 3.1.1.9 prior to administration of the study agents. No specific prophylactic or supportive care is necessary prior to administration of the study agents.

5.2.3.2 Subsequent treatment days

Laboratory parameters must be reviewed and must be within the ranges as listed in 3.1.1.9 prior to administration of the study agents. No specific prophylactic or supportive care is necessary prior to administration of the study agents, however, patients who have developed flu-like symptoms that were controlled with acetaminophen or non-steroidal anti-inflammatory drugs during previous treatments may be pre-treated with acetaminophen (650 mg PO) or ibuprofen (400-600mg PO) as per the investigator's discretion.

5.2.4 Preparation of the dosage form

Term	Percentage
Climate change	100
Global warming	98
Green energy	95
Carbon footprint	92
Sustainable development	88
Renewable energy	85
Emissions reduction	82
Green economy	78
Carbon tax	95

Term	Percentage (%)
GDP	95
Inflation	95
Interest rates	95
Central bank	95
Monetary policy	95
Quantitative easing	95
Inflation targeting	95
Interest rate hike	95
Interest rate cut	95
Interest rate parity	95
Nominal interest rate	95
Real interest rate	95
Nominal GDP	95
Real GDP	95
Nominal exchange rate	70
Real exchange rate	50
Nominal income	95
Real income	95

CONFIDENTIAL

CONFIDENTIAL
This document is confidential. Do not disclose or use except as authorized.

5.3 Administration

Treatment Description					
Agent	Treatment phase	Schedule	Premedications Precautions	Dose	Route
NeoVax (peptides + poly-ICLC)	Prime	Days 1, 4, 8, 15, 22*	None	Poly-ICLC: 4 x 0.5 mg (total dose 2 mg) Peptides: 4 x 300 μ g per peptide Vol = 4 x 1 ml	injections into 4 different anatomic sites (0.5 ml i.d. & 0.5 ml s.c.)
NeoVax (peptides + poly -ICLC)	Boost	Days 78 and 134**	None	Poly-ICLC: 4 x 0.5 mg (total dose 2 mg) Peptides: 4 x 300 μ g per peptide Vol = 4 x 1 ml	injections into 4 different anatomic sites (0.5 ml i.d. & 0.5 ml s.c.)

* \pm 3 day treatment window is allowed except for days 4 and 8 (\pm 1 day)

** \pm 7 day treatment window is allowed

5.3.1 Injections

Each of the up to 4 NeoVax syringes will be assigned to one of four extremities. At each immunization, each NeoVax syringe will be administered to the assigned extremity as follows: using one syringe/needle per site, 0.5 mL will be administered intradermally (i.d.) and 0.5 mL will be administered subcutaneously (s.c.) using the same syringe/needle at the same injection site (i.e. NeoVax A will be injected i.d. and s.c. into left arm on day 1, 4, 8 etc., NeoVax B will be injected i.d. and s.c. into right arm on days 1, 4, 8 etc.). Alternative anatomical locations for patients who are status post complete axillary or inguinal lymph node dissection or other contraindications that prevent injections to a particular extremity are the left and right midriff, respectively.

5.3.2 Treatment window

NeoVax may be administered within 1 day of the scheduled administration date for days 4 and 8, within 3 days of the scheduled administration date for days 15 and 22 and within 7 days for days 78 and 134.

5.3.3 Observation post vaccination

Patients should be observed in the clinic for at least 60 minutes after the last of the 4 injections and vital signs should be checked once between 30 and 90 minutes after the

CONFIDENTIAL

This document is confidential. Do not disclose or use except as authorized.

last injection for each clinic visit. Monitoring for immediate adverse events should include attention to possible injection site reaction or a systemic reaction. In the absence of the occurrence of an adverse event, patients will be discharged from the outpatient clinic.

5.4 Dose schema and staggering of patients

5.4.1 DLT and expansion cohorts

Five patients will be entered for the initial safety evaluation (Cohort 1). If two or more patients in Cohort 1 experience dose limiting toxicity (DLT) during the first 7 weeks of treatment, then that cohort will be determined to have unacceptable toxicity; otherwise, an additional 10 patients will be treated at the initial dose to increase the likelihood of detecting serious toxicities, to complete biologic correlative endpoints, and to gain preliminary experience with clinical tumor activity. If Cohort 1 is found to have unacceptable toxicity, then 5 patients may be enrolled on cohort -1 shown below. For Cohort -1, the dose of poly-ICLC is dropped by 50% relative to Cohort 1 but the dose of peptides remains the same. If two or more patients in Cohort -1 experience a DLT, then the study will be stopped. If none or only one patient experiences a DLT on Cohort -1, then 10 additional patients will be enrolled for additional toxicity evaluation, to complete biologic correlative endpoint, and to gain preliminary experience with clinical tumor activity. If four or more patients in the expansion cohort experience dose limiting toxicity (DLT) during the first 7 weeks of treatment, then that cohort will be determined to have unacceptable toxicity and further dosing of all patients will be stopped.

Dose De-escalation Schedule 1 cycle = 22days		
	Dose Level	Dose of poly-ICLC
	- 1	0.25 mg per injection site (4 injections, total dose 1 mg Vol = 4 x 0.875 ml)
Starting Dose →	1	0.5 mg per injection site (4 injections, total dose 2 mg)

5.4.2 Staggering of patients in DLT cohorts

5.4.3 The first three patients of Cohort 1 and Cohort -1 will be enrolled in a staggered fashion: Patients 2, 3 and 4 will not start treatment until the week after the previous

CONFIDENTIAL

This document is confidential. Do not disclose or use except as authorized.

patient has completed the priming phase (scheduled for day 22). **Prime/boost schedule**

Vaccine will be administered following a prime/boost schedule. Priming doses of vaccine will be administered on days 1, 4, 8, 15, and 22 as shown above (Section 5.3, Administration and Schema B). In the boost phase, vaccine will be administered on days 78 (week 12) and 134 (week 20).

5.4.4 Definition of evaluable patients

All patients receiving at least one dose of vaccine will be evaluable for toxicity. Patients will be evaluable for immunologic activity if they have received all vaccinations during the priming phase and the first boost vaccination.

A minimum of 3 vaccinations and absence of DLTs are required for a patient to complete the 7-week DLT observation period successfully.

5.5 Definition of Dose-Limiting Toxicity

Dose-limiting toxicity (DLT) is based on the CTEP Active Version (version 4.0) of the NCI Common Terminology Criteria for Adverse Events (CTCAE). DLT refers to toxicities experienced within 49 days (7 weeks) of treatment initiation (“DLT window”). If treatment has to be delayed because of a toxicity that does not fulfill the criteria of a DLT, the DLT window should be extended by that time period of delay. A DLT will be defined as follows:

1. Grade 3 or 4 toxicity that is definitely, probably, or possibly related to the administration of vaccine, excluding:
 - Transient (\leq 72 hours) flu-like syndrome;
 - Grade 3 nausea, vomiting, constipation, or diarrhea that returns to grade 2 (or lower) level within 48 hours;
 - Grade 3 rash that resolves to grade 2 or grade 1 within \leq 14 days.
2. Grade 3 or 4 abnormal laboratory value that is definitely, probably, or possibly related to the administration of vaccine if it persists for more than 7 days, requires hospitalization or medical intervention (except for Grade 3 electrolyte abnormality that lasts \leq 72 hours, is not clinically complicated, and resolves spontaneously or responds to conventional medical intervention).
3. Any grade 3 or grade 4 toxicity that is considered, in the opinion of the investigator, to be dose-limiting.
4. Any death related to study treatment.

CONFIDENTIAL

This document is confidential. Do not disclose or use except as authorized.

Management and dose modifications associated with the above adverse events are outlined in Section 6 (Expected Toxicities and Dosing Delays/Dose Modifications).

5.6 General Concomitant Medication and Supportive Care Guidelines

Acetaminophen or non-steroidal anti-inflammatory drugs (NSAIDS) may be used for prevention or treatment of flu-like illness symptoms. If clinically necessary, corticosteroids, antihistamines and non-steroidal anti-inflammatory drugs, including COX-2 inhibitors may be used at the discretion of the treating physician. Investigators may prescribe all other concomitant medications or treatments deemed necessary to provide adequate patient care.

Management of more serious toxicities will be directed by a study investigator and will be in accordance with standard of care clinical practice.

5.7 Duration of Therapy

Duration of therapy will depend on tolerability of the immunizations and evidence of disease recurrence as judged by the treating investigator. In the absence of treatment delays due to adverse events, treatment will be given until the day 134 vaccination (the 2nd booster vaccination) or until one of the following criteria applies:

- Disease recurrence, if it is deemed by the treating investigator to be in the best interest of the patient to discontinue study treatment;
- Intercurrent illness that prevents further administration of treatment
- Unacceptable adverse event(s);
- Patient demonstrates an inability or unwillingness to comply with protocol requirements;
- Patient decides to withdraw from the study; or
- General or specific changes in the patient's condition which render the patient unacceptable for further treatment in the opinion of the treating investigator.

5.8 Duration of Follow Up

Patients removed from study for unacceptable adverse events will be followed until resolution or stabilization of the adverse event.

Every 3 months (“close observation”) follow-up visits should continue until initiation of a new therapy for recurrent disease or withdrawal of consent, whichever occurs first, for a maximum of 2 years after the surgery. Patients will undergo disease restaging scans every 6 months for 2 years after the surgery.

CONFIDENTIAL

This document is confidential. Do not disclose or use except as authorized.

5.9 Criteria for Removal from Study

Patients will be removed from study when any of the criteria listed in Section 5.7 applies. The reason for study removal and the date the patient was removed must be documented in the study-specific case report form (CRF).

In the event of unusual or life-threatening complications, participating investigators must immediately notify the Principal Investigator, [name], PhD at DFCI

[REDACTED].

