6.3 Dose Modifications/Delays

- 6.3.1** If a patient develops grade 3 toxicity attributable to the vaccine, additional treatment will be withheld until the toxicity has resolved or improved to grade 1. If the toxicity constitutes a DLT as defined in 5.5, the patient will be removed from the study. If the toxicity does not fulfill the criteria of a DLT, the next vaccine administration may be delayed for a maximum duration of 14 days. If vaccine dosing has to be delayed more than 2 times because of a toxicity that is not considered a DLT, the patient will be removed from the study.
- 6.3.2** If a patient develops grade 4 toxicity attributable to the vaccine (with the exception of certain grade 4 laboratory abnormalities as defined in section 5.5), he or she will be removed from treatment.
- 6.3.3** If two or more grade 4 or greater toxicities attributable to the vaccine are observed, the trial will be suspended to investigate the causes of these (unexpected) toxicities.

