14.2 Analysis of Secondary Endpoints

Secondary endpoints in this clinical trial will: (a) assess the induction of IFN- γ T-cell response to the total peptide pool, and (b) estimate the proportion of patients alive without disease progression at two years after resection. Analyses of these secondary endpoints will be based on the 15 patients treated at the recommended vaccine dose.

The induction of IFN- γ T-cell response will be based on ELISPOT assessments taken prior to vaccine administration and at week 16. The proportion of patients who achieve more than 55 SFU/ 10^6 PBMC *or* 3 times their baseline level will be presented with a 90% exact binomial confidence interval. Based on a cohort of size 15, the confidence interval will be no wider than 0.46.

The proportion of patients alive, without disease progression at two years after resection will be estimated using the method of Kaplan-Meier. The endpoint will be calculated as the time between pathological confirmation of complete resection and the first of disease recurrence or death. Patients who are disease-free at the time of study reporting will have their follow-up censored at the time of the last study visit. Patients who were disease-free at the time of their last assessment and who have either been lost to follow-up or withdrawn consent will have their follow-up censored at the time of the last study assessment. The proportion of patients alive and disease-free at two years will be presented with 90% confidence intervals estimated using log(-log(DFS)) methodology.

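### Sections 5.9 and 6.3.1 remove patients from study when vaccination stops, while 5.8, 10.1.1 and calendar footnote 17 keep dosed patients in recurrence follow-up

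*Combined protocol and SAP*

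**What the plan says.** Section 5.7 (Duration of Therapy) governs vaccination: "treatment will be given until the day 134 vaccination (the 2nd booster vaccination) or until one of the following criteria applies". Six criteria follow: recurrence (where the investigator judges stopping to be in the patient's interest), intercurrent illness, unacceptable adverse events, non-compliance, the patient's decision to withdraw, and a change in condition.

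Section 5.9 uses the same list for a different purpose: "Patients will be removed from study when any of the criteria listed in Section 5.7 applies". Section 6.3.1 adds "If the toxicity constitutes a DLT as defined in 5.5, the patient will be removed from the study" and applies the same consequence after more than two toxicity delays. Section 6.3.2, on grade 4 toxicity, says instead that "he or she will be removed from treatment".

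Section 5.8 has two paragraphs. The first says "Patients removed from study for unacceptable adverse events will be followed until resolution or stabilization of the adverse event". The second says that three-monthly "follow-up visits should continue until initiation of a new therapy for recurrent disease or withdrawal of consent, whichever occurs first", up to two years after surgery, and that "Patients will undergo disease restaging scans every 6 months for 2 years after the surgery".

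The two-year endpoint is in 14.2: "The proportion of patients alive, without disease progression at two years after resection will be estimated using the method of Kaplan-Meier". The analysis set is the 15 patients treated at the recommended dose.

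**The concern.** Stopping vaccine and leaving the study are different events, and the plan gives no rule for which text governs when they conflict. Nothing says that a patient removed under 5.9 or 6.3.1 stays in recurrence follow-up. If a site stops scans and visits at removal, that patient contributes nothing after the last assessment. Section 14.2 would in effect censor the patient there, because it offers no other handling.

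The proportion alive without progression at two years is a named secondary objective (1.3.2) and rests on 15 patients, so each lost patient costs precision. Patients who stop for illness or a worsening condition may also have a different recurrence risk from those who continue, in which case the censoring is informative. Follow-up that was never done cannot be restored at analysis.

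**Working it through.** **Step 1: the passages side by side.**

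| Place | Status on stopping vaccine | Recurrence follow-up |
|---|---|---|
| 5.9 | off study | not mentioned |
| 6.3.1 (DLT, more than two delays) | off study | not mentioned |
| 5.8, first paragraph | off study, for adverse events | only adverse-event follow-up named |
| 6.3.2 (grade 4) | off treatment | not mentioned |
| Calendar footnote 12 | off active treatment; leukapheresis or blood draw still due | not mentioned |
| 5.8, second paragraph | no exception for stoppers | until new therapy for recurrence or consent withdrawal, at most 2 years |
| Calendar footnote 17 | no exception for stoppers | same, plus death |
| 10.1.1 | any patient with one dose | evaluable for recurrence |
| 14.2 | not mentioned | no censoring category for removal |

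The first three rows, read literally, end participation. Footnote 17, 10.1.1 and the second paragraph of 5.8 do not.

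**Step 2: which criteria matter.** Recurrence is already the endpoint event. Withdrawal of consent ends follow-up under any wording. That leaves four of the six: illness, adverse events, non-compliance and change in condition.

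**Step 3: stated figures.** The plan gives no precision or dropout figure for the two-year estimate. The nearest figure is the maximum width of 0.46 that 14.2 gives for the 90% exact interval of the ELISPOT proportion. It reproduces: at 8/15 the interval is 0.300 to 0.756, a width of 0.456.

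**Step 4: precision with full follow-up.** Take 5 of 15 disease-free, S = 0.333, and the log(-log) method of 14.2.
- Standard error on that scale: √(S(1−S)/15) / (S·|ln S|) = 0.1217/0.3662 = 0.332.
- Multiplier: exp(1.645 × 0.332) = 1.73.
- 90% interval: S^1.73 to S^(1/1.73), or about 0.15 to 0.53.

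**Step 5: effect of censoring at removal.**
- From the documents: n = 15, and two-year recurrence of 60–80% for stage IIIB/IIIC (Section 2.2). This gives a true disease-free proportion S of 0.20 to 0.40 if deaths without recurrence are ignored.
- Assumed: k = 1 to 3 patients are removed at 0.4 year (about 21 weeks) after surgery if still event-free; their later hazard is HR = 0.5 to 3 times that of the others; event times are exponential.

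With f = k/15, solve for λ in

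e^(−0.4λ) · [(1−f)·e^(−1.6λ) + f·e^(−1.6·HR·λ)] = S.

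If removed patients are censored at 0.4 year, Kaplan-Meier tends to e^(−2λ). Example with k = 3, HR = 2, S = 0.30: λ = 0.541, since 0.805 × (0.8×0.421 + 0.2×0.177) = 0.300. The estimate tends to e^(−1.082) = 0.339.

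Expected estimate for a true value of 0.30:

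| Removed | HR 0.5 | HR 1 | HR 2 | HR 3 |
|---|---|---|---|---|
| 1 of 15 | 0.288 | 0.300 | 0.313 | 0.318 |
| 2 of 15 | 0.275 | 0.300 | 0.326 | 0.337 |
| 3 of 15 | 0.263 | 0.300 | 0.339 | 0.358 |

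With 3 removed, a true 0.20 gives 0.165 (HR 0.5) to 0.244 (HR 3), and a true 0.40 gives 0.364 to 0.466.

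**Step 6: check by simulation** (n = 15, 10,000 runs, true value 0.30). With follow-up kept, the mean is 0.30 throughout. With 3 censored, it is 0.339 at HR 2 and 0.357 at HR 3. At equal hazards the mean stays at 0.30, but the SD rises from 0.118 to 0.122 (1 removed), 0.118 to 0.126 (2) and 0.119 to 0.131 (3, about 10%).

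**The case against.** The strongest reply is that recurrence follow-up is already provided for. The second paragraph of 5.8 and footnote 17 set end points for visits, and stopping vaccine is not among them. Section 10.1.1 keeps every dosed patient evaluable. Footnote 12 schedules a procedure after active treatment has stopped. Section 12.1.2 has a follow-up and survival form apart from the off-treatment/off-study form. The first paragraph of 5.8 can be read as setting adverse-event follow-up alone; it does not say that other follow-up ends. Section 14.2 names no censoring at removal.

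All of this stands, and it rules out the stronger reading that a reader might infer from 5.9, namely that the plan requires early stoppers to lose recurrence follow-up. That is one reading of a contradiction. The contradiction remains, because other text supports the literal reading: 6.3.1 and 6.3.2 use different terms in adjacent paragraphs, Section 6 refers to an off-study visit after which patients may be contacted about toxicity, and one form serves both statuses.

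A reader might also infer that the two-year estimate would come out too high. The documents do not support a direction. They give neither the number removed nor those patients' recurrence risk, and a hazard ratio below 1 reverses the sign. The shift is also small against the interval, and the endpoint is secondary, descriptive and without a decision rule.

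**Conclusion.** The point holds as an internal contradiction with a possible cost to a secondary endpoint. It affects patients who stop vaccine for illness, adverse events, non-compliance or a change in condition. If 5.9 or 6.3.1 is followed literally, they could be censored months after surgery. Precision then falls even at equal hazards, with an SD about 3% to 10% higher for 1 to 3 patients.

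Bias is possible but not established. For a true 30%, it is about +1 to +6 points at two to three times the hazard, zero at equal hazard, and about -1 to -4 points at half the hazard. These figures depend on the assumed number and timing of removals, the hazard ratio and the exponential model. The reason to act is that the lost data cannot be recovered and the correction is cheap.

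**What to change.** Reconcile 5.7, 5.8, 5.9 and 6.3.1 by defining two statuses, off vaccination and off study, each with its own date and reason on the case report form.
- **5.7:** leave the treatment-stopping criteria unchanged. For a patient who decides to withdraw, record whether this covers vaccination only or follow-up as well.
- **5.9:** keep removal from study for withdrawal of consent to follow-up, and for the follow-up end points already in 5.8 and footnote 17.
- **6.3.1 and the first paragraph of 5.8:** use the off-vaccination status, and say that adverse-event follow-up is in addition to recurrence follow-up.
- **5.8 and footnote 17:** state that the planned three-monthly visits, six-monthly scans and survival status continue to two years for all other vaccinated patients. Align the time origin too: 5.8 counts from surgery and footnote 17 from treatment initiation.
- **14.2:** state that stopping vaccine is not a reason for censoring.

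The cost is wording in these sections, and follow-up visits and scans that are already planned continue for the few patients who stop early.
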